 Alcohol or substances of abuse (Y/N) (specify the substance) 	
 Previous experience of pain NRS ≥5 for 7 days (Y/N) 	

Preoperative evaluation (60 to 1 day before the scheduled procedure)

Presence of chronic pathologies (Y/N) (if yes, provide the list of medications)
Pharmacological treatments including supplements or nutraceuticals (continuous in the last 3 months)

(Y/N) (if yes, provide the list of drugs)

- Chronic pain (NRS \geq 3 for \geq 3 months) (Y/N)
- Neuropathic pain (Y/N) (assessment via questionnaire)*
- Pain catastrophizing (Y/N) (assessment via questionnaire)*
- Anxiety (Y/N) (assessment via questionnaire)*
- Depression (Y/N) (assessment via questionnaire)*
- Presence of pain in the last three days (NRS ≥3 mean pain intensity in the 24 hours) (Y/N)

*Questionnaires

- Evaluation of neuropathic pain: Douleur Neuropathique en 4 questions (DN-4)
- Pain Catastrophizing: Pain Catastrophizing Scale (PCS)
- Anxiety: General Anxiety Disorder-7 (GAD-7)
- Depression: Beck Depression Inventory (BDI)-II

Evaluation of the perioperative period

Evaluation before surgery

• Site of surgery

Head

Vertebral column

Arms/legs

Chest

Abdomen

Genitourinary system

• Surgical technique

Open surgery

- Minimally invasive surgery
- Robotic surgery
- ERAS (enhanced recovery after surgery) protocol (Y/N)
- Anesthesiologic technique
- **General Anesthesia**
- Spinal Anesthesia
- **Epidural Anesthesia**

Peripheral nerve block

- Preventive/protective analgesia (Y/N)
- Premedication (Y/N)
- OFA opioid-free anesthesia protocol (Y/N)
- Postoperative analgesic prescription (Y/N)

Evaluation after surgery

- Pain NRS score \geq 3 at the end of the surgery (Y/N)
- Presence of pain (NRS \geq 5 average value in the 24 hours) in the region of the operation at rest or during movement after surgery (Y/N)
- Analgesic prescription after surgery

≤12 hours of coverage

13-24 hours of coverage

- ≥ 24 hours of coverage
- Postoperative surgical complications (Y/N)
- Postoperative infectious complications (Y/N)
- Mobilization after surgery ≤6 hours? (Y/N)

Postoperative period (third month after surgery)

• Pain assessment: average pain intensity assessed using a standard NRS scale (the cutoff score will be set at \geq 3 mean pain intensity over the last three days) (Y/N).

• Diagnosis of CPSP (the pain is localized in the surgical field or in the area of the lesion, projected into the innervation territory of a nerve located in this area, or referred to a dermatome) (Y/N)

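### As printed, the age and analgesic-coverage bands overlap at 55 years and 24 hours, and four questionnaire predictors are reduced to yes/no with no stated cut-off

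*Combined protocol and SAP*

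**What the plan says.** **Bands.** Under Preoperative evaluation, the protocol groups age as 18 to 35, 36 to 55, and 55 or over. Under Evaluation after surgery, analgesic coverage has three groups: "≤12 hours of coverage", "13-24 hours of coverage" and "≥ 24 hours of coverage". The lowest of the three BMI bands is printed with a less-than-or-equal sign in front of the range 18.5 to 24.9.

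**Questionnaires.** Four preoperative items are yes/no and refer to a named instrument:

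- "Neuropathic pain (Y/N) (assessment via questionnaire", from DN-4
- "Pain catastrophizing (Y/N) (assessment via questionnaire", from PCS
- "Anxiety (Y/N) (assessment via questionnaire", from GAD-7
- "Depression (Y/N) (assessment via questionnaire", from BDI-II

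No cut-off for any of them appears in the document. Other yes/no items do carry one, for example "Previous experience of pain NRS ≥5 for 7 days (Y/N".

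**Use.** Development of the risk index and Statistical analysis of results screen the items one by one, apply backward elimination at 0.05, turn the parameters of the resulting model into points, choose a high-risk cut-off score, and tabulate the CPSP proportion at each index value. Power analysis allows for 15 parameters, or 12 in the reduced 10% incidence scenario, and plans at least 1500 patients.

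**The concern.** The product of this study is a points index, which needs exactly one code per patient per item. Where two bands share a value, two people who both follow the protocol can code the same patient differently.

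A yes/no item drawn from a questionnaire without a cut-off is a wider problem, because it can touch any patient and not only those at a boundary. The document does not say whether total scores are stored, or whether the reduction to yes/no is done centrally. With at least 10 centres, a yes may not mean the same thing everywhere. A later user could not reproduce the item, which sits badly with the protocol's commitment to TRIPOD. A cut-off chosen after seeing the data would also add optimism.

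Reducing a score to yes/no discards information as well, even when the cut-off is stated.

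**Working it through.** **1. Categories that contain each value, as printed.**

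| Item | Value | Matching bands |
|---|---|---|
| Age | 54 | 1 |
| Age | 55 | 2 |
| Age | 56 | 1 |
| Coverage, h | 12 | 1 |
| Coverage, h | 12.5 | 0 |
| Coverage, h | 23 | 1 |
| Coverage, h | 24 | 2 |
| Coverage, h | 25 | 1 |

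The gap between 12 and 13 hours matters only if fractions of an hour are recorded. A BMI of 17 has one band if the lowest band means 24.9 or less, and none if it means 18.5 to 24.9.

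**2. Thresholds on yes/no predictors.** The five NRS predictors are previous pain, chronic pain, pain in the last three days, pain at the end of surgery, and 24-hour postoperative pain. With mobilization, 6 of 6 have a printed threshold. Of the four questionnaire predictors, 0 of 4 have one.

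**3. The plan's sample size, and whether the point touches it.** The shrinkage criterion is n = P / [(S − 1) ln(1 − R²cs/S)]. S = 0.9 is assumed, since the plan does not state it. R²cs is taken as 0.15 × its maximum.

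- Incidence 50%, P = 15: maximum 0.75, R²cs = 0.1125, n = 15 / [−0.1 × ln(0.875)] = 1123.3, so 1124 (stated 1124).
- Incidence 10%, P = 15: maximum 0.478, rounded to 0.48, R²cs = 0.072, n = 15 / [−0.1 × ln(0.92)] = 1798.96, so 1799 (stated 1799). Without rounding it is 1807.
- Incidence 10%, P = 12: 1439.2, so 1440 (stated 1440). Without rounding it is 1446.

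The calculation depends on the number of parameters, not on how a predictor is coded. A yes/no questionnaire item and a linear total both use one parameter, so four instruments use four either way. The point does not change the sample size.

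**4. Patients affected, N = 1500.** The shares are assumptions; the documents give none.

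- Exactly 55 years, 1 to 2.5%: 1500 × 0.01 = 15 to 1500 × 0.025 = 37.5, so 15 to 38.
- Exactly 24 hours of coverage, 5 to 50%: 75 to 750. The range is wide because 24 is a round number and may be common; it bounds the size only loosely.
- Two cut-offs that differ by 5 to 20 percentage points in the share coded yes: 75 to 300 patients per questionnaire.

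**5. What a differing cut-off does to the meaning of yes.** Assume a normal score, an odds ratio of 1.5 per standard deviation, and 10% incidence. If the top 10% are coded yes, their CPSP risk is 17.6%. If the top 15% are, it is 16.5%; if the top 30% are, 14.5%. The difference is 1.1 to 3.1 percentage points over the same 5 to 20 point range. This is illustrative only.

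**The case against.** **The index does not exist yet.** Only items that survive screening and elimination receive points. A reader might infer that every patient's index score is already undefined; the documents do not support that. The effect on the score is conditional on selection, although selection itself runs on these codes.

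**Coverage may never be scored.** Statistical analysis of results describes elimination among preoperative and intraoperative predictors, while coverage is listed after surgery. The separate models by time point may still include it, so this is unsettled. The overlap in the printed bands remains.

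**Most of the model might seem to be affected.** A reader might count the questionnaires, age, BMI and coverage as 4 × 1 + 3 × 2 = 10 parameters and set them against the 12 or 15 in Power analysis. That is the wrong denominator. The listed predictors come to about 15 + 15 + 7 = 37 parameters (preoperative, before surgery, after surgery; single choice for site, technique and anaesthesia; free-text lists excluded), so the share is 10/37 = 27%, and it mixes time points that may not be modelled together.

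**The eCRF may already settle it.** All data enter one REDCap database, and the data manager sends queries to centres. Methods for continuous variables are planned although every listed predictor is banded, nominal or yes/no, and the three-month DN-4 is listed without yes/no. Both are compatible with stored scores. The eCRF is not in the documents, so divergent coding between centres is a possibility and not a demonstrated fact.

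**BMI.** The odd symbol may come from text extraction, and as the lowest of three bands it reads naturally as everything below 25. It needs confirmation only.

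**Conclusion.** The point holds. The age and coverage bands are not mutually exclusive as printed, and four yes/no predictors have no cut-off, against the protocol's own practice for the NRS items and mobilization. The missing cut-offs matter more than the overlaps, because they are not confined to boundary patients.

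The consequence for a patient's score depends on two things: the item being selected, and the eCRF not already storing raw values with central coding. The patient counts rest on assumed shares. The outcome is unaffected, because its NRS threshold is stated. This should be corrected, but it does not threaten the study as a whole.

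**What to change.** 1. Make the bands exclusive and exhaustive: for example, age 18–35, 36–54, and 55 or over in completed years; coverage up to 12, over 12 to under 24, and 24 hours or more. Confirm that the lowest BMI band means below 25.
2. Record age in years, BMI, hours of coverage and each questionnaire's total score in the eCRF, and say so in the predictor list. Enter the questionnaire totals as linear terms, one parameter each as now, which avoids the information lost by dichotomizing. Splines for age, BMI or coverage are optional and not needed to resolve the ambiguity.
3. Where the points score needs a yes/no version, pre-specify one cut-off per questionnaire and apply it centrally.
4. State which variables the planned continuous-variable methods apply to.

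**Cost.** If raw values are already stored, only protocol text and band limits change. If not, seven fields become numeric; the questionnaires are already administered. Turning linear terms into points takes one extra step. Patients already entered may need back-filling. That is feasible only if the local investigator's matching key, described under Data collection, is available; Ethical considerations says that database records cannot be linked to patients, so the two statements need to be reconciled first.

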The outcome variable is the presence of CPSP assessed 3 months after surgery and defined as an average pain intensity of at least 3 on the NRS scale (11-point one-dimensional pain scale) in the last three days, and pain localized to the surgical field (or in the lesion area) projected into the innervation territory of a nerve located in this area or referred to a dermatome.

Separate prediction models will be developed using data derived from surveys conducted at the relevant time points for the development of the risk index.

The sample size of the development dataset must be large enough to develop a prediction model equation that is reliable when applied to new individuals in the target population. The Authors estimate to include approximately 1500 patients to develop a clinical prediction model of CPSP three months after surgery.

The Authors estimate that at least 10 Centers are needed to enroll the intended study population.

The total expected time, from the date of project approval to the production of the draft manuscript, is 24 months.

Background

Chronic post-surgical pain (CPSP) is a common and disabling postoperative complication; it is defined as pain that develops or increases in intensity after surgery and persists at least 3 months after surgery. It can

be localized in the surgical field, projected into the innervation territory of a nerve located in this area, or referred to a dermatome [1].

CPSP affects millions of individuals worldwide, with an estimated incidence between 10 and 50%, depending on the surgery performed [2]. It is rated serious by 2-10% of patients [2;3]. Furthermore, CPSP is considered a serious medical but also social and economic problem [4;5] and represents a significant portion of medical prescriptions and healthcare costs [6]. Furthermore, in combination with psychological consequences, chronic pain significantly impairs the quality of life [7] and productivity, exposing patients to the risk of drug addiction [8].

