Several risk factors for CPSP have been established [9;10;11]. A wide interindividual range characterizes the sensation of pain; multiple factors influence the perception of pain, such as genetic determinants, neurological diseases affecting the central or peripheral nervous system, inflammatory modulation of tissues, and the presence of inflammatory mediators, as well as the experience of pain [12;13;14;15; 16]. CPSP is widely associated with iatrogenic nerve lesions and chronicity is also linked to the remodeling of the central nervous system which determines central sensitization phenomena [17;18]. Furthermore, psychological factors such as depression, pain catastrophizing, mood, and stress could influence the perception of pain [19;20;21;22].

Although surgery is a determining factor in the onset of chronic pain, some patient characteristics also appear to be predictive of an increased risk of persistent pain: young age [23], female sex [24], preoperative pain [25], high levels of acute postoperative pain [25] and psychosocial factors [26;27]. The most significant limitations of current awareness in this field are the heterogeneity of study methodology, including assessment of pain timing, different definitions of pain, and the small sample size of most of the previous studies.

Identifying risk factors for CPSP before surgery could help identify high-risk patients using risk prediction models and allocate preventative strategies [28;10]. Identification of risk groups in the patient population is critical to providing individualized pain treatment [29] and may help reduce long-term opioid use.

The present study aims to identify the risk factors of CPSP three months after surgery and, to develop a valid risk index to detect high-risk patients that considers the multifactorial etiology of CPSP.

Aim

The main objective of this multicenter observational study is to estimate the occurrence of CPSP three months after any type of surgery and identify risk factors for the development of a multivariate clinical prediction model of CPSP at three months.

Methods

This is a multicenter, prospective, observational study on adult patients requiring any type of surgical procedure. This study is designed and will be reported according to the STrengthening the Reporting of OBservational studies in Epidemiology (STROBE) statement. Ethics Committee approval is mandatory to begin registration at all recruitment centers.

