- Surgical complications (Y/N)
- Infectious complications related to surgery (Y/N)
- Malignancy (Y/N)

Questionnaires:

• Douleur Neuropathique in 4 questions (DN-4)

Outcome variable

The outcome variable is the presence of CPSP assessed 3 months after surgery and defined as an average pain intensity of at least 3 points on the NRS scale (one-dimensional pain scale - from 0 to 10 points) in the last three days and pain localized to the surgical field (or in the lesion area) projected into the innervation territory of a nerve located in this area, or referred to a dermatome [30;31].

Development of the risk index

Separate prediction models will be developed using data derived from investigations conducted at the relevant time points.

(1) Primary version of the risk index, made up of items derived from a systematic bibliographic search (compilation of the item pool).

(2) In a second phase, the Authors will analyze the associations between each of these indices and the probability of CPSP 3 months after surgery (dichotomous variable), evaluated using logistic regression models.

(3) Items that were found to be significant in the bivariate analyses will then be analyzed multivariately (logistic regression models).

(4) In a fourth step, the Authors will safeguard the results of the multivariate analyses by calculating the area under the ROC curve of the model, and then, the cut-off score for a high risk of developing CPSP will be identified with an optimal compromise between sensitivity and specificity.

(5) Finally, the items that will generate significant predictive factors in the logistic regression analyses will be collected into an index. For each value of this index, the Authors will calculate the proportion of patients who reported CPSP at 3 months after surgery.

Statistical analysis of results

The study population will be described by summarizing the variables collected in each period of evaluation of the subject (preoperative, perioperative before surgery, perioperative after surgery, three months post-operatively after surgery). In particular, the discrete variables will be reported in terms of absolute and relative frequency, and the continuous variables will be summarized via mean and standard deviation or via median and interquartile range, based on the symmetry of each distribution.

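### The protocol lists the pain-score items, including month-3 pain, only as yes/no against fixed cut-offs and provides nowhere for storing the 0-10 value

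*Combined protocol and SAP*

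**What the plan says.** Under Data collection, six items rest on an NRS threshold, and all six are listed as yes/no:

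- Preoperative evaluation: previous pain experience (at least 5, for 7 days), chronic pain (at least 3, for 3 months or more) and pain in the last three days (at least 3).
- Evaluation after surgery: pain at the end of surgery (at least 3), and a 24-hour average of at least 5 "in the region of the operation at rest or during movement after surgery (Y/N", which is one answer covering both conditions.
- Postoperative period (third month after surgery): "average pain intensity assessed using a standard NRS scale (the cutoff score will be set at" at least 3, "mean pain intensity over the last three days) (Y/N".

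Outcome variable gives the matching definition: CPSP is "defined as an average pain intensity of at least 3 points on the NRS scale (one-dimensional pain scale - from 0 to 10 points", together with a localisation requirement. Development of the risk index then models "the probability of CPSP 3 months after surgery (dichotomous variable), evaluated using logistic regression models". Statistical analysis of results plans no description of pain severity and no analysis at another cut-off. The only questionnaire listed at month 3 is the DN-4, which the protocol uses to assess neuropathic pain, not intensity.

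**The concern.** A yes/no answer can always be derived from a score, but a score cannot be recovered from a yes/no answer. Two of the study's aims are touched.

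The first is the occurrence of CPSP, which is part of the main objective. Background lists among the main limits of earlier work "different definitions of pain, and the small sample size of most of the previous studies". With a single stored threshold, the study could not re-express its incidence at another cut-off for comparison, nor show whether the predictors and the index hold up when the cut-off moves. Background also cites a severity figure ("It is rated serious by 2-10% of patients"), to which these data could offer no counterpart.

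The second is the prediction model. Background names preoperative pain and high acute postoperative pain as predictors. Both would enter as threshold indicators only, so any gradient within either side of the cut-off is unavailable to the model.

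**Working it through.** **1. What each stored answer can distinguish.** This follows from the cut-offs alone.

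- Month 3, cut-off 3: scores of 3 and 9 give the same answer, so severity among cases is invisible. A case definition at 4 or above cannot be formed.
- 24-hour average, cut-off 5: 0 and 4 give the same answer, as do 5 and 10.
- End of surgery, cut-off 3: 0 and 2 coincide, but 0 and 4 do not.
- Last-three-days preoperative pain and month-3 pain, both cut at 3: a patient going from 3 to 8 and one going from 8 to 3 give the same pair of answers. Background defines CPSP to include pain that increases after surgery. The preoperative item is not tied to the surgical site, so numeric scores would only partly resolve this.

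**2. Is a numeric value provided for elsewhere?** Data collection, Outcome variable, Development of the risk index and Statistical analysis of results contain no such item. The sentence that "the continuous variables will be summarized via mean and standard deviation" is generic and names no pain score.

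**3. The plan's own sample sizes.** Inputs from Power analysis: 15% of variability explained, incidence 50% or 10%, 15 or 12 parameters. A shrinkage target S = 0.9 is assumed, because the protocol does not state one.

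- n = P / [(S − 1) ln(1 − R²/S)], with R² = 0.15 × its maximum.
- The maximum is 1 − exp{2[p ln p + (1 − p) ln(1 − p)]}, which is 0.750 at 50% and 0.478 at 10%.
- 50%, 15 parameters: R² = 0.1125; 15 / (0.1 × 0.1335) = 1123.3, so 1124 as stated.
- 10%, 15 parameters: R² rounded to 0.072; 15 / (0.1 × 0.08338) = 1799, as stated (1807 without rounding).
- 10%, 12 parameters: 12 / (0.1 × 0.08338) = 1439.2, so 1440 as stated (1446 without rounding).

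These depend on the number of parameters, the incidence and the explained variability assumed. The form in which pain is stored is not an input. A linear NRS term uses one parameter, as a yes/no term does.

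**4. Illustration of the predictor loss.** Assume a normally distributed score with a linear effect and a single cut, with a proportion p of patients above it. The information kept is φ(z)² / [p(1 − p)], where z is the normal quantile at 1 − p.

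- p = 0.5: 0.3989² / 0.25 = 0.637, about 64%.
- p = 0.3: 0.3477² / 0.21 = 0.576, about 58%.
- p = 0.2: 0.2800² / 0.16 = 0.490, about 49%.

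The documents give neither p nor the shape of any NRS distribution, so none of these is an estimate for this study.

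**The case against.** The eCRF is not among the documents, and the protocol says only that web-based forms will be used. The month-3 line says intensity is assessed on an NRS and that a cut-off will be set, which can be read as a score that is obtained and then cut. Age and BMI are also listed as categories, yet the analysis section plans means, standard deviations and t-tests. The list may therefore show analysis categories rather than field types. This stands as far as it goes: a reader might infer that the scores are thrown away, but the documents show only that no storage is provided for.

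The outcome is prespecified and consistent across the abstract, the month-3 item and Outcome variable. Severe CPSP is not a stated objective, and complaining of differing definitions is compatible with choosing one and keeping to it. That is also right, and the point does not ask for a different outcome. It does not answer the inability to test how much the results depend on that choice.

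Simple yes/no items suit a bedside points index. That argument applies to the finished index, not to what is collected: cut-offs for scoring can be set later from numeric data.

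The change is not wholly free. Scoring rest and movement separately needs a second score and, if both are modelled, another parameter. At 10% incidence the plan needs 1440 patients for 12 parameters and 1799 for 15, against about 1500 planned, so there is little room. The previous-pain and chronic-pain items are history questions that can be answered without a current score. The fix is limited accordingly.

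**Conclusion.** The point holds, conditional on capture as listed. In that case month-3 severity and sensitivity to the cut-off of 3 are unavailable, and graded preoperative and acute pain is reduced to threshold indicators. The outcome part needs no distributional assumption. The predictor part is real in direction, but its size cannot be computed from the documents. The 64%, 58% and 49% figures rest on normality, linearity, a single cut and assumed proportions above it.

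Three stronger readings are not supported:

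- A reader might turn the illustration into a 36% to 51% loss of acute-pain information in this study. No NRS distribution is given, the plan has two acute items at different times and cut-offs whose joint retention was not calculated, and no loss in the C-statistic was calculated.
- A reader might see a contradiction between planned summaries of continuous variables and yes/no pain items. The sentence is generic and promises nothing about pain.
- A reader might conclude that the outcome or the sample size is wrong. Neither is affected.

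This is a cheap improvement worth making. The planned analysis can run without it, but severity not recorded at capture cannot be reconstructed from the yes/no answers.

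**What to change.** - Record the 0-10 NRS in the eCRF for last-three-days preoperative pain, end of surgery, the 24-hour average and month 3. If the eCRF already stores these values, say so in the protocol and use them.
- Derive the outcome centrally from the month-3 score and the localisation item, with the cut-off of 3 unchanged.
- Enter the preoperative and acute scores as single linear terms in place of the corresponding yes/no terms, so that the candidate-parameter count does not rise. The two history items can stay yes/no.
- Prespecify a sensitivity analysis at a higher outcome cut-off (for example, at least 4) and a description of month-3 severity.
- Separate scores at rest and on movement are optional. If one 24-hour score is kept, state which condition it refers to.

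The cost is four changed eCRF fields and slightly more analysis. Separating rest from movement would add one score and, if both are modelled, one parameter.

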The treatments will be performed according to the rules and ethical standards on human experimentation and the Helsinki Declaration of 1964 (further revised in 2013). All study participants will provide written informed consent (including all the information about possible risks and side effects) for participation in the study. Every precaution will be taken to protect patient privacy.

For the development and validation of the prognostic models, the guidelines on prognostic modeling studies of individual participant data and the recommendations of the Transparent Reporting of a multivariable predict model for Individual Prognosis or Diagnosis (TRIPOD) will be followed.

➢ Population
 Inclusion criteria:
 Age ≥18 years
 Patients scheduled for elective surgery
 Exclusion criteria:
 Patients with perceptive (or sensorial) alterations of pain

Patients unable to communicate

Cognitive impairment

Insufficient knowledge of the Italian language.

Data collection

Recruitment is competitive. Each participating Center undertakes to include at least 20 patients in the study. Patients will participate in the study voluntarily and will not receive compensation of any kind from anyone, either directly or indirectly. Competitive enrollment means that being a multicentric research project, the number of patients included by each participating Center may vary depending on the inclusion capacity of each. There is therefore no maximum limit to the number of patients that each Center can include. The inclusion of patients in the study will end as soon as the total number of subjects described by the protocol is reached.

Web-based electronic case report forms (CRFs) will be used to collect data. All data will be anonymous and only the local principal investigator could match patients and reference numbers.

A comprehensive item pool was derived from a systematic literature search.

Data collection will record parameters at four different times:

- preoperative evaluation
- evaluation of the perioperative period (before surgery)
- evaluation of the perioperative period (after surgery)

• postoperative period

As regards the post-operative follow-up (three months after surgery), a telephone or outpatient evaluation is foreseen at the discretion of each center.

Preoperative evaluation (60 to 1 day before the scheduled procedur	e)
• Age	
18-35	
36-55	
≥55	
• Sex	
Female	
Male	
• BMI	
≤18.5 - 24.9	
25 - 29.9	
≥30	

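### The month-3 CPSP outcome rests on a Yes/No diagnosis with no named assessor and no separation from the predictor data, so attribution of pain to surgery may depend on the predictors and bias their effects

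*Combined protocol and SAP*

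**What the plan says.** Under Outcome variable, CPSP at three months has two parts. The patient must have "average pain intensity of at least 3 points on the NRS scale" over the last three days, and the pain must lie in the surgical or lesion area, be projected along a nerve from it, or be referred to a dermatome.

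The item list under Postoperative period (third month after surgery) gives each part as a Yes/No. Intensity is "mean pain intensity over the last three days) (Y/N"). Location is "Diagnosis of CPSP (the pain is localized in the surgical field or in the area of the lesion", followed by the nerve-territory and dermatome alternatives. No separate item asks where the pain is.

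Under Data collection, "a telephone or outpatient evaluation is foreseen at the discretion of each center", and "All data will be anonymous and only the local principal investigator could match patients and reference numbers". The assessment thus sits with the centre, and no central assessment is described. The centre's own forms hold the predictors, including acute pain "in the region of the operation at rest or during movement after surgery (Y/N"), "Pain catastrophizing (Y/N) (assessment via questionnaire"), anxiety, depression, chronic pain and neuropathic pain.

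No section names the month-3 assessor, limits what that person may see, supplies a script, or plans adjudication. Background names preoperative pain, acute postoperative pain and psychosocial factors as expected predictors.

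**The concern.** The location item calls for judgement. Chronic and neuropathic pain before surgery are candidate predictors, not exclusion criteria, so for some patients someone must decide whether month-3 pain belongs to the operation, possibly by telephone. An assessor who knows of severe early pain or a positive questionnaire may probe harder and attribute more readily. One who knows of long-standing pain may attribute to that instead.

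Either way, the error would differ between predictor groups. According to Statistical analysis of results, predictors stay in the model at 0.05 and its parameters become the scores, so a biased coefficient affects both which items enter the index and their weight. Bootstrapping corrects optimism from overfitting. Every resample carries the same recorded outcome, so it cannot show this bias.

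**Working it through.** **The plan's own figures.** It gives none for assessment error. Its sample sizes are not in dispute. With n = P/[(S−1)·ln(1−R²/S)], S = 0.9 (assumed) and R² = 0.15 × its maximum (0.75 at 50% incidence, 0.478 at 10%), I get 1124, 1807 and 1446, against the stated 1124, 1799 and 1440. Rounding 0.478 to 0.48 gives the last two exactly. Masking would not change them.

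**Inputs from the protocol.** N = 1500; incidence scenarios 10% and 50%; two-sided 0.05; both outcome parts required.

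**Assumptions.** A binary predictor is present in 30% (450 vs 1050 patients) and has no true effect. The share a with NRS ≥3 is the same in both groups: 20%, 35% or 60%. Among those patients, Yes is ticked with probability t1 if the predictor is present and t0 if not. The documents supply none of these rates.

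**Formulas.** Observed risks are q1 = a·t1 and q0 = a·t0, and OR = [q1/(1−q1)] / [q0/(1−q0)]. The chance of a significant result in the positive direction is Φ[(q1 − q0 − 1.96·SE₀)/SE₁], with SE₀ pooled and SE₁ unpooled.

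| t1 vs t0 | a | q1 vs q0 | OR | Chance of p<0.05, positive |
|---|---|---|---|---|
| 75% vs 70% | 20% | 0.150 vs 0.140 | 1.08 | 8% |
| | 35% | 0.2625 vs 0.245 | 1.10 | 11% |
| | 60% | 0.450 vs 0.420 | 1.13 | 19% |
| 80% vs 70% | 20% | 0.160 vs 0.140 | 1.17 | 18% |
| | 35% | 0.280 vs 0.245 | 1.20 | 30% |
| | 60% | 0.480 vs 0.420 | 1.27 | 57% |
| 85% vs 65% | 20% | 0.170 vs 0.130 | 1.37 | 53% |
| | 35% | 0.2975 vs 0.2275 | 1.44 | 81% |
| | 60% | 0.510 vs 0.390 | 1.63 | 99% |

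With equal ticking the OR is 1.00 and the chance is the nominal 2.5%. Overall incidence in these scenarios runs from about 14% (0.3 × 0.17 + 0.7 × 0.13) to 44% (0.3 × 0.48 + 0.7 × 0.42), inside the plan's 10–50%. The last column is for an unadjusted test of one predictor, so it is only a guide to the backward elimination.

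**Opposite direction.** If known prior pain lowers ticking to 65% vs 70%, then at a = 20% the OR is (0.13/0.87)/(0.14/0.86) = 0.92, and at a = 60% it is (0.39/0.61)/(0.42/0.58) = 0.88.

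**Is error alone enough?** No. With the same error in both groups (sensitivity 95%, specificity 97% for the whole outcome), a true OR of 1 stays at 1.00 and a true OR of 2 falls to 1.72–1.89. Bias away from a null effect needs unequal ticking.

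**The case against.** The strongest reply is that the protocol is silent on masking, and silence is not evidence of unmasked assessment. That stands. A reader might infer that the month-3 diagnosis is made by the same staff with the earlier forms open, but no section says who completes it or what REDCap access applies. Step 5 of Development of the risk index speaks of patients reporting CPSP, which leans towards patient report. What can be said is that the separation is not specified, and that it cannot be relied on across at least 10 centres.

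The second reply concerns size, and it also stands. A reader might apply an extra false-positive rate d to every non-case, so that the exposed risk is p + (1−p)d. With d = 2 or 5 points this gives OR 1.20 or 1.53 at p = 10%, and 1.07 or 1.18 at p = 30%. The arithmetic is right, but it counts patients with NRS <3, whom the two-part definition excludes. At p = 10% and d = 5 points, the added risk is 0.90 × 0.05 = 4.5 points. If 20% have NRS ≥3, it must come from the 10% with pain elsewhere, of whom 45% would be wrongly ticked.

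Third, a fixed upward direction cannot be claimed, since the abstract and Background define CPSP as pain that begins or worsens after surgery, and known prior pain may prompt a No.

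Fourth, a reader might see a breach of the reporting recommendations cited under Methods ("For the development and validation of the prognostic models, the guidelines on prognostic modeling studies of individual participant data", and TRIPOD). Their content is not in the documents, so the point does not rest on them.

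Finally, age, sex, BMI and surgical site are much less exposed than the pain and questionnaire items.

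**Conclusion.** The concern holds as an unprotected route to bias, not as bias shown to occur. As listed, the month-3 items give a judged Yes/No and a dichotomised intensity, with no raw answer from which the outcome could be re-derived and no separation from predictors that the protocol itself expects to matter.

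Through the location tick alone, a null predictor would show an OR of 1.08–1.13 if ticking differs by 5 points among patients with NRS ≥3, and 1.17–1.27 if it differs by 10. The corresponding chance of passing p<0.05 in the positive direction is 8–19% and 18–57%. ORs of about 1.4–1.6 need a 20-point gap. These figures rest on assumed ticking rates, a 30% predictor prevalence and an NRS ≥3 share of 20–60%. Inflation is the main worry, though dilution or reversal is possible for preoperative pain. An interviewer might also influence the NRS answer, which these figures leave out.

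The outcome should be tightened, because raw answers not collected at month 3 cannot be reliably recovered later.

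**What to change.** 1. Ask intensity and location from one fixed script at every centre, by telephone or in clinic, or send the items as a patient survey link.
2. Store the raw 0–10 NRS and the location answer, and derive CPSP from them by a rule written in advance that covers projected and referred pain.
3. Where nerve territory or dermatome needs clinical judgement, make it from the stored answers without the predictor forms.
4. Set REDCap rights so that the month-3 form is completed without access to the preoperative and perioperative forms, and where feasible by someone who did not collect them. State in the protocol who assesses.

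The cost is a script, a few extra fields, a derivation rule and a user-rights setting on the platform already chosen. The sample size does not change and no additional assessor is required. There are two downsides. Masking stays incomplete where the interviewer knows the patient, and patient-reported location is coarser for projected or referred pain.
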